6.4 Demographic and Baseline Characteristics

Demographic/baseline variables include age, sex, ethnicity, race, and height at screening, weight at screening and baseline, and medical history. Tabular summaries of the demographic/baseline variables will be presented for the safety, ITT, and PP populations, except for medical history, which will be summarized for the safety population only.

6.5 Subject Disposition

A disposition of subjects will include the number and percentage of subjects in each of the following categories:

- Subjects in the randomized population
- Subjects in the ITT population
- Subjects treated (safety population)
- Subjects in the PP study population

Within each of the previous categories, the number and percentage of subjects who completed and discontinued from the study will be summarized. The reasons for study discontinuation will also be summarized. The reason for discontinuation may include any of the following:

- Subject withdrew consent
- Lost to follow-up
- Administrative reason
- Adverse event
- Investigator decision
- Failure to follow required study procedures
- Other

Only one (primary) reason for study discontinuation will be recorded for each subject.

6.6 Protocol Deviations

Protocol deviations will be presented in listings. If applicable, the number and percent of subjects within each type of protocol deviation will be presented using discrete summary statistics. Protocol deviations will include, but are not limited to:

- Non-compliance with any scheduled study visit
- Non-compliance with study treatment
- Disallowed concomitant medications
- Non-compliance with study inclusion or exclusion criteria
- Non-compliance with study assessment procedures

6.7 Study Medication Exposure and Compliance

Duration of exposure is defined as the total number of days a subject is exposed to any study treatment. This will be calculated for each subject by taking the difference between the date of last dose *minus* the date of the first dose, *plus* 1 (date of last dose – date of first dose +1).

Duration of Treatment exposure will also be summarized using descriptive statistics (n, mean, SD, median, minimum, and maximum).

Percent of study drug compliance is defined as $\{(\text{number of tablets dispensed} - \text{number of tablets returned}) / 2 * (\text{date of last dose} - \text{date of first dose} + 1)\} * 100\%$.

For each treatment, SM compliance will be summarized by compliance category (<80%, 80-120%, and >120%) and number of subjects in each compliance category. Study medication compliance will also be summarized as a continuous variable using descriptive statistics (n, mean, standard deviation, median, minimum, and maximum) for each treatment.

Summaries of treatment compliance and exposure will be presented separately for the Titration Period, Maintenance Period, and combined Titration and Maintenance Periods.

6.8 Concomitant Medications

Concomitant medications will be assigned an 11-digit code using the World Health Organization Drug Dictionary (WHO DD) drug codes. Concomitant medications will be further coded to the appropriate Anatomical-Therapeutic-Chemical (ATC) code indicating therapeutic classification. A tabular summary of concomitant medications by drug class will be presented for the safety population.

6.9 Efficacy Analyses

6.9.1 Primary Efficacy Analysis

The primary efficacy endpoint is the percent change (PCH_T) in the frequency (unweighted score) of IA behaviors per 7 days in the Treatment (Titration and Maintenance) period relative to the Baseline period calculated over the number of days with non-missing IA diary data. The frequency of IA behaviors per 7 days is the sum of scores for all events in a given period of sequential days, adjusted to 7 days.

The primary efficacy endpoint PCH_T will be calculated by $PCH_T = 100 * (T - B) / B$, where T and B are IA behavior frequencies per 7 days during the Treatment period and baseline period, respectively. The IA behavior frequency per 7 days is defined as $(\text{SUM} / \text{DAY}) * 7$, where SUM is the sum of the IA behaviors reported in the subject IA diary, and DAY is the number of days with non-missing IA frequency data in the subject IA diary during the specified study period.

Let μ_1 , μ_2 , and μ_3 represent the median percent change in the frequency of IA behaviors per 7 days in the Treatment period relative to the Baseline period in the ITT population for subjects treated with Placebo, 18 mg and 36 mg doses of SPN-810, respectively. The null (H_0) and the alternative (H_a) hypotheses are as in the following.

- $H_{01}: \mu_2 = \mu_1$, (there is no difference between the median of the 18 mg dose SPN-810 and the median of placebo) vs. $H_{a1}: \mu_2 \neq \mu_1$, (there is a difference between the median of the 18 mg dose SPN-810 and the median of placebo)
- $H_{02}: \mu_3 = \mu_1$, (there is no difference between the median of the 36 mg dose SPN-810 and the median of placebo) vs. $H_{a2}: \mu_3 \neq \mu_1$, (there is a difference between the median of the 36 mg dose SPN-810 and the median of placebo)

The primary efficacy analysis will be performed using the Wilcoxon rank-sum test to compare the medians of each of the two doses of SPN-810 (18 mg and 36 mg) with the median of the Placebo. The Hodges-Lehmann estimate and the associated 95% confidence interval (CI) will be calculated. To preserve the overall Type I error-rate at 0.050 for the primary efficacy endpoint, multiplicity adjustment due to interim analysis and two comparisons of SPN-810 dose group (18 mg and 36 mg) with the Placebo will be performed as described in [Section 10.1.4](#).

6.9.2 Secondary Efficacy Analyses

The secondary endpoints are:

1. Actual Caregiver CGI-I score at Visit 6
2. Actual Investigator CGI-I score at Visit 6
3. Change from Visit 3 to Visit 6 in Investigator CGI-S score
4. Change from Visit 3 to Visit 6 in CHQ-28 score
5. Change from Visit 3 to Visit 6 in PSI-4-SF scores in:
 - a. Parental Distress
 - b. Parent-Child Dysfunctional Interaction
 - c. Difficult Child
6. Change from Visit 3 to Visit 6 in SNAP-IV ADHD scores in:
 - a. Inattention ratings
 - b. Hyperactivity/Impulsivity ratings
 - c. Combined Scale ratings

Each one of the six secondary endpoints will be analyzed using the analysis of covariance method based on the ITT population with missing data imputed using the Last Observation Carried Forward (LOCF) method. The model includes treatment and baseline as fixed independent covariates and change from baseline to final maintenance visit as a response variable. The least squares mean of each treatment group, the difference in the least squares mean (18mg dose minus placebo and 36 mg dose minus placebo), and the 2-sided 95% CI for the difference will be obtained.

To preserve the overall type I error rate at 0.05 for the secondary endpoints, a sequential testing procedure will be used with the following features. First only dose or doses that are significantly different from placebo for the primary endpoint will be tested for secondary endpoints. The first of the secondary endpoints will be compared to placebo using the Hochberg step up procedure but only using those doses retained as a result of testing the primary endpoint (Hochberg 1988). The second secondary endpoint will be tested in the same manner but only using those doses that were retained from the

primary and the first secondary endpoint and so forth. As the endpoints are gone through in the pre-defined order doses will only be retained if significant for all endpoints tested so far and at the given stage the Hochberg step-up procedure will be applied.

The ordering of the 6 secondary endpoints from first to be tested to sixth is: Investigator Clinical Global Impression – Improvement Scale (CGI-I)(Endpoint 1), Clinical Global Impression – Severity Scale (CGI-S) (Endpoint 2), Child Health Questionnaire (CHQ-28) (Endpoint 3), Parenting Stress Index (PSI-4-SF) (Endpoint 4), Caregiver-completed CGI-I (Endpoint 5) and SNAP-IV Rating Scale (Endpoint 6).

6.9.3 Sensitivity Analysis

In the presence of a high drop-out rate, performance of sensitivity analysis is crucial. The purpose of sensitivity analysis is to see whether different methods of handling missing data provide consistent and similar results for the primary efficacy analysis. To this end, the three sensitivity analyses will be performed:

1. Multiple imputation under MAR using available data on the primary endpoint
2. Placebo- based imputation under MNAR
3. Per Protocol Analysis

6.9.3.1 *Multiple imputation under Missing at Random (MAR)*

The multiple imputation (MI) method assumes that the missing data are missing at random (MAR), that is, the probability that an observation is missing may depend on the observed values but not the missing values. For example, if a subject's Diary values are available on Day 1 and Day 2 but missing on Day 3, then the missing value on Day 3 is related to the non-missing value on Day 1 and Day 2.

MI is implemented using the following three steps.

- 1) SAS PROC MI is applied with input dataset containing some missing values for all days during the titration and maintenance period to create 100 datasets. The data sets will include separate columns for the frequency of incidences during each day starting from baseline. The Markov Chain Monte Carlo (MCMC) method will be used to complete the missingness pattern to a monotone pattern separately by treatment arm. The monotone patterns will be achieved by applying sequential imputation based on Bayesian regression with the treatment arm included as a covariate. All copies contain identical values of the non-missing data items, but different values imputed for missing values.
- 2) For each of these MI data sets, the percent change will be computed as in the observed data set and the primary analysis based on the Wilcoxon rank-sum test will be conducted and asymptotic 95% confidence intervals will be constructed.
- 3) To produce a single confidence interval for each dose placebo comparison (e.g., Dose 1 versus placebo), PROC MIANALYZE will be used and Rubin's combination rules will be applied to the treatment effect estimates and associated asymptotic standard errors from the MI data sets.

The treatment effect estimates will be defined as the midpoints of the asymptotic confidence intervals and the standard errors will be defined as the asymptotic standard errors (based on the width of the associated 95% confidence intervals) from the Hodges-Lehmann estimate of the individual datasets (Rubin 1987).

6.9.3.2 *Multiple imputation under Missing Not at Random (MNAR)*

This approach can be labeled “worst-case” sensitivity analyses as it assumes that after discontinuation subjects from the dosing arms would adopt the outcome model estimated from the placebo arm. To generate missing values from this “placebo-based” imputation model, PROC MI with the MNAR statement (available in SAS 9.3 and later versions) will be used or, alternatively, SAS macros available at the DIA Missing Data Working Group site (Ratitch et al., 2013; Ayele et al., 2014) can be used.

6.9.3.3 *Per Protocol Analysis*

This analysis will be conducted by repeating the primary analysis on the per protocol population.

6.10 Sample Size and Power Considerations

Based on results from the Phase 2 study, it is assumed that the average treatment difference between SPN-810 dose groups and placebo is 11.51 with a common standard deviation of 27.3. A sample size of 132 subjects per arm (264 subjects for 3 arms) will yield 90% power to detect a non-zero difference between the median of 18 mg or 36 mg dose group and the placebo using the Wilcoxon rank-sum test with a 2-sided significance level alpha=0.05.

It is assumed that approximately 20% of subjects will dropout before the completion of the study and hence, an adjusted total of 330 subjects will be randomized in a 1:1:1 ratio to obtain 264 subjects in the ITT population at the completion of the study.

The sample size was calculated using the nQuery Advisor Software, Version 7.

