2. CGI-S
3. CHQ-PF28
4. PSI-4-SF
5. Caregiver-rated CGI-I
6. SNAP-IV Rating Scale

Safety and Tolerability Endpoints

1. Adverse events (AE)
2. Extrapyramidal symptoms (EPS) scales (Simpson-Angus Scale, Barnes Akathisia Scale, Abnormal Involuntary Movement Scale)
3. Clinical laboratory tests (Hematology, Chemistry and Urinalysis)
4. ECGs
5. Vital signs
6. Columbia Suicide Severity Rating Scale (C-SSRS)
7. Infrequent Behaviors Checklist

Sample size:

Based on results from the Phase 2 study, it is assumed that the average treatment difference between SPN-810 dose groups and placebo is 11.51 with a common standard deviation of 27.3. A sample size of 132 subjects per arm (264 subjects for 3 arms) will yield 90% power to detect a non-zero difference between the median of 18 mg or 36 mg dose group and the placebo using the Wilcoxon rank-sum test with a 2-sided significance level alpha=0.05.

It is assumed that approximately 20% of subjects will dropout before the completion of the study and hence, an adjusted total of 330 subjects will be randomized in a 1:1:1 ratio to obtain 264 subjects in the ITT population at the completion of the study.

The sample size was calculated using the nQuery Advisor Software, Version 7.

Analysis Populations:

Safety Population: will include all randomized subjects who received at least 1 dose of study drug.

Intent-to-Treat (ITT) Population: will include all subjects who received at least 1 dose of study drug and have a baseline and at least 1 valid post-randomization assessment of frequency of IA behaviors based on IA diary entry.

Per-Protocol (PP) Population: will include all of the subjects in the ITT population who completed the treatment period with 80% diary completion compliance and who did not have major protocol deviations.

PK population: will include all subjects in the safety population who had at least one PK sample drawn which had a quantifiable concentration for at least one analyte of interest.

Hypotheses:

Let μ_1 , μ_2 , and μ_3 represent the median percent change in the frequency of IA behaviors per 7 days in the Treatment period relative to the Baseline period in the ITT population for subjects treated with Placebo, 18 mg and 36 mg doses of SPN-810, respectively. The null (H_0) and the alternative (H_a) hypotheses are as in the following.

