1 INTRODUCTION

The purpose of this statistical analysis plan (SAP) is to ensure the credibility of the study findings by specifying the statistical approaches to the analysis of the data prior to database lock. This SAP covers the planned analyses of all data collected on the eCRFs and diary pages, and will identify handling of data issues. The statistical analysis plan presented in this document will supersede the statistical analysis methods described in the clinical protocol. Any deviations/changes from the planned analyses described in this SAP will be identified, with justification, in the appropriate section of the clinical study report. This SAP is based on the clinical study protocol 810P301, version 9.0, dated 01 November 2018 and its associated electronic case report forms (eCRF).

This SAP does not cover the analytic methods for the determination of Minimal Clinically Important Change (MCIC) in clinical efficacy. The assessment of MCIC will be performed by [REDACTED], which is a designated CRO to perform this analysis. This SAP also does not cover the methods for the population pharmacokinetic modeling and analysis.

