3.3.4 Blinding

Subjects, all site personnel, the Sponsor and its designated Contract Research Organizations (CROs) are blinded with the following exceptions. The CRO and Sponsor personnel who are

involved in the randomization generation, study drug supply, and PK concentration assays are unblinded. However, they are not involved in the routine study monitoring, data cleaning and review, the design of this SAP or data analysis.

3.4 *Hypotheses*

The null and alternative hypotheses are:

- H_{01} : There is no difference between SPN-810 █ mg and Placebo in the treatment of IA in subjects with ADHD in conjunction with standard ADHD treatment.
- H_{a1} : There is a difference between SPN-810 █ mg and Placebo in the treatment of IA in subjects with ADHD in conjunction with standard ADHD treatment.
- H_{02} : There is no difference between SPN-810 █ mg and Placebo in the treatment of IA in subjects with ADHD in conjunction with standard ADHD treatment.
- H_{a2} : There is a difference between SPN-810 █ mg and Placebo in the treatment of IA in subjects with ADHD in conjunction with standard ADHD treatment.

3.5 *Determination of Sample Size*

Based on results from the Phase 2 study, it is assumed that the average treatment difference between SPN-810 dose groups and placebo is 15 with a common standard deviation of 27.3 in the primary efficacy endpoint. A sample size of 77 subjects per arm (231 subjects for 3 arms) will yield 90% power to detect a non-zero difference between the median of active drug group █ mg or █ mg dose) and the placebo group using the Wilcoxon rank-sum test with a 2-sided significance level $\alpha=0.05$.

It is assumed that approximately 20% subjects will dropout before the completion of the study and hence, an adjusted total of 291 subjects will be randomized in a 1:1:1 ratio to obtain 231 subjects in the ITT population at the completion of the study.

To estimate the variability for designing Study 810P503, the standard deviation (SD) of the primary endpoint for Study 810P301 was reviewed blindly. This review indicates that the SD for interim data was actually 34.83 instead of the protocol-assumed 27.3 (see above). This increase in the SD resulted in the increase in the sample size to 122 subjects per treatment. Allowing for 20% dropout, the final sample size for randomization is 153 subjects per treatment.

The sample size was calculated using the nQuery Advisor Software, Version 7.

3.6 *Changes to Analyses Planned in the Protocol*

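### Protocol 6.10 and SAP 3.5 size the same trial on different inputs (11.51 with SD 27.3; 15 with SD 34.83), and the protocol's 90% power for 11.51 does not survive the SAP's SD

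*Protocol*

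**What the plan says.** **Protocol 6.10** states: "it is assumed that the average treatment difference between SPN-810 dose groups and placebo is 11.51 with a common standard deviation of 27.3". It continues with "A sample size of 132 subjects per arm (264 subjects for 3 arms", and says this number "will yield 90% power to detect a non-zero difference between the median of 18 mg or 36 mg dose group and the placebo". The calculation is for a two-sided Wilcoxon rank-sum comparison at 0.05. Allowing 20% dropout, it randomises 330 in a 1:1:1 ratio to leave 264 in the ITT population. The synopsis repeats the pair: the difference "is 11.51 with a common standard deviation of 27.3".

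**SAP 3.5** states: "it is assumed that the average treatment difference between SPN-810 dose groups and placebo is 15 with a common standard deviation of 27.3", and derives 77 per arm for 90% power. A later paragraph reports a blinded look at the endpoint's variability, made to help design another study: "This review indicates that the SD for interim data was actually 34.83 instead of the protocol-assumed 27.3". The SAP then gives 122 per treatment and, with 20% dropout, 153 randomised per treatment. It restates neither the difference nor the power at that step.

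**SAP 1** says: "This SAP is based on the clinical study protocol 810P301, version 9.0". The SAP's summary of changes also ties the new SD paragraph to protocol amendment V9.0. The protocol text reviewed here carries a log of changes made to V8.0, so I take it to be version 9.0.

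The value 34.83 does not appear in the protocol, and 11.51 does not appear in the SAP. Both documents introduce their difference as a Phase 2 result.

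**The concern.** Taking 15 and 27.3 as the common starting point, each document moves one input and leaves the other. The protocol has the smaller difference with the unchanged SD. The SAP has the unchanged difference with the larger SD. Someone holding both cannot say which difference the trial has 90% power to detect.

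The SAP also describes the SD behind the protocol's calculation as contradicted by the trial's own data, which bears directly on the protocol's power statement. At stake is how a null result would be read. At the SAP's SD and 122 to 132 evaluable per arm, a true 11.51-point effect would be missed about 26% to 29% of the time, not 10%.

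**Working it through.** **Inputs.** Differences: 11.51 (Protocol 6.10) and 15 (SAP 3.5). SDs: 27.3 (both) and 34.83 (SAP 3.5). Test: Wilcoxon rank-sum, two-sided 0.05 (both). Numbers per arm: 132 (Protocol 6.10), 122 (SAP 3.5), and 88 from the protocol's totals (330/3 = 110; 110 × 0.8 = 88 = 264/3).

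**Formulas.** Both documents cite nQuery but give no formula. I assume a normal shift and use Noether's method:

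- P = Φ(d / (SD × √2))
- n per arm = (1.96 + 1.2816)² / [6 (P − 0.5)²]
- power = Φ(√(6n) × (P − 0.5) − 1.96)

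**Step 1: reproduce the stated figures.**

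- Protocol: 11.51/27.3 = 0.422, P = 0.6172. At 132 per arm, √792 × 0.1172 − 1.96 = 1.34, so power is 91.0%. Exactly 90% needs 127.5 per arm, so 132 is slightly conservative.
- SAP starting point: 15/27.3 = 0.549, P = 0.6512, n = 76.6, stated as 77.
- SAP revision: 15/34.83 = 0.431, P = 0.6196, n = 122.4, stated as 122. Then 122/0.8 = 152.5, stated as 153.

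With 11.51 in place of 15, the SAP's revision would have needed about 205 per arm. Of the two printed differences, only 15 returns 122.

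**Step 2: put the SAP's SD under the protocol's difference.** 11.51/34.83 = 0.330, P = 0.5924.

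| Evaluable per arm | 11.51, SD 27.3 | 11.51, SD 34.83 | 15, SD 34.83 |
|---|---|---|---|
| 88 (330 randomised, 20% dropout) | 76.8% | 56.5% | 78.5% |
| 122 (SAP) | 88.7% | 70.5% | 89.9% |
| 132 (Protocol) | 91.0% | 73.9% | 92.0% |

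For 11.51 with SD 34.83, the asymptotic-efficiency approximation (n × 3/π) gives 57.2%, 71.3% and 74.7% in the same row order. A 20,000-run simulation gives 56.7%, 71.8% and 73.8%. Power of 90% for that pair needs about 202 to 206 per arm, depending on the method.

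**Step 3: are the two pairs one revision written two ways?** Holding the SAP's standardised effect and returning to SD 27.3 gives 15 × 27.3/34.83 = 11.76, not 11.51. That is close but not an exact rescaling, and the numbers per arm differ as well (132 and 122).

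**Step 4: could blinding explain the larger SD?** If 34.83 pools three equal arms and both doses truly differ from placebo by 11.51, the between-arm variance is 11.51² × 2/9 = 29.4. The within-arm SD is then √(34.83² − 29.4) = 34.4. Power for 11.51 becomes about 72% at 122 and 75% at 132.

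**Step 5: multiplicity.** All figures above are per comparison, before the Hochberg and combination-test adjustment. At 0.025, a Bonferroni bound, power for 11.51 with SD 34.83 is about 61% at 122 and 65% at 132 (asymptotic-efficiency method).

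**The case against.** The strongest reply is that neither document assumes 11.51 with SD 34.83. A power statement is conditional on its own SD, and the protocol's pair does deliver its 90% at 132 per arm. That stands: Protocol 6.10 contains no arithmetic error on this point. What remains is that the sponsor's own later document reports that the conditioning SD was not borne out.

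A second reply is that the plan admits the uncertainty. Protocol 6.11 and SAP 6.5 say the Phase 2 endpoint was R-MOAS change, not percent change in diary frequency, and provide sample-size re-estimation. The planning inputs do not enter the final test or the stage weights, and the result will be reported with a Hodges-Lehmann estimate and 95% CI. This limits the consequence: Type I error is untouched. It does not explain why two documents that should agree after re-estimation print different inputs.

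A third reply is that the SAP supersedes the protocol. Protocol 6.1 says so for analysis methods, but requires changes to principal features to go into a protocol amendment, and the protocol still prints 27.3.

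A reader might also infer that one of the two Phase 2 attributions must be untrue. The documents do not prove it. The Phase 2 endpoint was different, the Phase 2b study had several dose groups, and part of Protocol 1.3 is redacted. The change log attributes the revision to 11.51 to re-estimation, which makes a leftover label plausible, no more than that.

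**Conclusion.** The inconsistency is real and in current text. Each pair is internally sound, but they are different pairs for the same trial, and the SAP's SD undercuts the protocol's power statement. If 34.83 is right, power for 11.51 is about 71% at 122 per arm, 74% at 132 and 57% at 88. On the protocol's totals, even 15 points at SD 34.83 has only about 78% power.

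These figures assume a normal shift, an unadjusted two-sided 0.05 test for one dose against placebo, and the stated evaluable numbers. The ITT definition keeps anyone with one dose, a baseline and one valid post-randomisation diary assessment, so evaluable numbers could exceed these. With nobody lost, power for 11.51 at SD 34.83 would be about 66% at 110 per arm and 80% at 153, still short of 90%.

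Two stronger readings should be resisted. One is that 71% to 74% is the trial's power: it crosses the protocol's difference with the SAP's SD, and it depends on a number per arm that the documents have not settled. The other is that the SAP claims 90% power at 122 per arm. It states 90% only for 77 per arm at 15 with SD 27.3; the pair behind 122 is inferred from the arithmetic.

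**What to change.** State one difference and one SD in Protocol 6.10, the synopsis and SAP 3.5, each with its true source (Phase 2, the re-estimation, or the blinded review). Keep the Phase 2 attribution only for a figure that came from Phase 2. Check Protocol 6.11 and SAP 6.5 in the same pass, since both repeat that the effect size came from Phase 2.

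Restate the power for that pair at the number per arm the trial will actually enrol. If the other difference remains of interest, give its power too.

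Do this together with the enrolment conflict: 132 per arm, 264 evaluable and 330 randomised in the protocol, against 122 evaluable and 153 randomised per arm in the SAP. Three arms of 132 are 396, not 264, and the SAP's 153 × 3 = 459 is 129 more than 330. Do not write into the protocol that 122 per arm gives 90% power while it still randomises 330, because that total leaves 88 per arm.

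The cost is wording in three main places and a less favourable power figure for at least one difference. The correction is to the stated figures; whether to enrol more subjects is a separate decision for the sponsor.

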4 STUDY METHODS

4.1 Selection of Study Population

The target population will be male and female subjects aged 6 to 12 years with IA and ADHD. SM will be administered in conjunction with the subject's standard ADHD treatment. Approximately 330 subjects will be randomized in this clinical investigation.

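### Protocol 6.10 counts 132 per arm as 264 for three arms, so 330 randomised 1:1:1 gives 88 evaluable per arm and about 77% power, not 90%; SAP 3.5 sets a different target

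*Protocol*

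**What the plan says.** Protocol 6.10 makes four linked statements, and the synopsis repeats them.

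- Assumptions: "it is assumed that the average treatment difference between SPN-810 dose groups and placebo is 11.51 with a common standard deviation of 27.3".
- Size and power: "A sample size of 132 subjects per arm (264 subjects for 3 arms) will yield 90% power to detect". What is to be detected is any difference in medians for each dose against control, and the stated test is as follows: "using the Wilcoxon rank-sum test with a 2-sided significance level alpha=0.05".
- Dropout: "approximately 20% of subjects will dropout before the completion of the study".
- Enrolment: "an adjusted total of 330 subjects will be randomized in a 1:1:1 ratio to obtain 264 subjects in the ITT population".

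Protocol 4.1 repeats the total: "Approximately 330 subjects will be randomized in this clinical investigation". Protocol 3.2 and 3.2.2.1 still randomise equally to 18 mg, 36 mg and placebo.

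SAP section 1 ties the SAP to a protocol version: "This SAP is based on the clinical study protocol 810P301, version 9.0, dated 01 November 2018". SAP 3.5 nevertheless starts from a difference of 15 with SD 27.3, giving 77 per arm, 231 in three arms and 291 randomised. It then reports a blinded SD of 34.83, raises the requirement to 122 per treatment, and concludes: "Allowing for 20% dropout, the final sample size for randomization is 153 subjects per treatment".

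**The concern.** The per-arm number and the total in protocol 6.10 cannot both be right for three arms. The randomised number is built on the total, so the error carries into the enrolment target. If sites stop at 330 with equal allocation, each dose-placebo comparison has two thirds of the evaluable subjects that the power claim assumes (88 against 132).

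The SAP does not settle the matter. It names the protocol version it rests on but uses a different difference, a different SD and a different target. A reader cannot tell from the two documents how many children are to be randomised, in how many arms, or with what power.

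**Working it through.** **Inputs.** Protocol 6.10: difference 11.51, SD 27.3, two-sided alpha 0.05, Wilcoxon rank-sum, 20% dropout, 330 randomised 1:1:1. SAP 3.5: difference 15, SD 27.3 and then 34.83.

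**Formulas (Noether).** With d = difference/SD and p = Φ(d/√2):

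- n per arm = (z₀.₉₇₅ + z₀.₉₀)² / [6(p − 0.5)²], where (1.960 + 1.282)² = 10.507
- power = Φ(√(6n) × (p − 0.5) − 1.960)

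**1. The protocol's per-arm figure.** d = 11.51/27.3 = 0.4216 and p = 0.6172.

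- n for 90% power = 10.507/(6 × 0.1172²) = 127.5, so 128 per arm.
- At 132: √792 × 0.1172 − 1.960 = 1.338, which gives 91.0%.

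The claim of 90% at 132 per arm is sound and slightly generous.

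**2. The protocol's totals.**

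- 3 × 132 = 396, while 2 × 132 = 264.
- 264/0.8 = 330 = 2 × 165, so the dropout step is right for 264 but covers two arms.
- Three arms of 132 evaluable need 396/0.8 = 495 randomised, or 165 per arm.

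**3. Power of the design as written.** 330/3 = 110 randomised per arm, and 110 × 0.8 = 88 evaluable.

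| Analysed per arm | Noether | Simulated rank-sum test (normal data, 20,000 runs) |
|---|---|---|
| 88 | 76.8% | 77.6% |
| 110 (no losses) | 85.3% | 86.0% |
| 132 | 91.0% | 91.5% |

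At 88 the calculation is √528 × 0.1172 − 1.960 = 0.733. A plain normal approximation with no rank-test penalty gives 79.9% at 88. Even a one-sided test would need 97 per arm for 90% by that approximation, so no standard convention makes 88 sufficient.

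**4. The SAP's figures.**

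- 15/27.3 gives 76.6, matching the stated 77; 3 × 77 = 231 is multiplied correctly. 77/0.8 rounds up to 97, and 3 × 97 = 291.
- 15/34.83 gives 122.4, against the stated 122. SAP 3.5 does not repeat the difference beside the new SD, but 15 is the value that reproduces its number.
- 122/0.8 = 152.5, rounded up to 153. Totals: 3 × 153 = 459 and 2 × 153 = 306.

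The SAP is internally consistent, but it agrees with 330 under neither arm count.

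**5. Two side scenarios, on which the conclusion does not rest.**

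- If one dose had to succeed alone at 0.025, power at 88 per arm would be about 67%. This is a fixed-sample approximation; the planned test combines stage-wise Hochberg p-values.
- If the protocol's difference (11.51) and the SAP's SD (34.83) both held, 132 per arm would give about 74%. Neither document pairs these two inputs.

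**The case against.** The strongest reply is that 264 and 330 are two-arm totals left beside stale wording. They fit two arms of 132 and 165 exactly. Protocol appendix 10.1.3 and SAP 6.5.6 allow a dose to be dropped at the interim. The protocol's change log attributes the new figures to sample size re-estimation. The SAP's change list says 3.5 covers changes to sample size and randomisation scheme after the interim, and SAP 7.7.7 introduces the secondary analyses as comparing a single dose with placebo. On this reading, power at 132 per arm is about 91%. It is lower if 330 includes Stage 1 subjects in a dropped arm. Assuming 48 such subjects (about half of the earlier 97 per arm), (330 − 48)/2 = 141 randomised and 141 × 0.8 ≈ 113 evaluable per arm gives about 86%.

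The reading is plausible, but the current text contradicts it. Protocol 6.10 says three arms, equal allocation and either dose; protocol 3.2 and 3.2.2.1 and SAP 3.1 and 7.7.1 still describe two doses and placebo. Neither document says that an arm was dropped. The SAP's two-arm total would still be 306, not 330.

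A second reply is that the ITT definition needs only one dose, a baseline and one post-randomisation diary assessment, so many dropouts would be analysed. That is fair, and 77% is therefore at the low end. But 6.10 itself equates 264 with the ITT count after dropout, and analysing all 110 per arm still gives only about 85%.

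Third, the two documents' standardised effects are close (0.422 and 0.431), so their per-arm requirements, 132 and 122, are not far apart. That stands. The larger conflict lies in the arm count and the totals.

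**Conclusion.** The concern holds and needs correcting in both documents. The power claim is right for 132 per arm; the three-arm total and the randomised number built on it are wrong. With three arms, 330 randomised 1:1:1 and 20% dropout, power per comparison is about 77%, rising to about 85% if no subject is lost from the analysis. It does not reach 90%. This assumes the protocol's difference and SD, a normal shift model and two-sided 0.05 before multiplicity adjustment. If a dose was in fact dropped, power would be about 91%, or about 86% under the Stage 1 assumption above, and the error would then be in the stated arm count and allocation. Either way, protocol 6.10 contradicts itself, and SAP 3.5 gives a target that matches it in neither two nor three arms. The primary test and its Type I error control are not affected.

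**What to change.** State one treatment difference, SD, number of arms, per-arm evaluable number, randomised total and power, identically in the protocol synopsis, 4.1 and 6.10 and in SAP 3.5.

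- **If three arms continue with 330 at 1:1:1:** give 110 randomised and 88 evaluable per arm, and restate power as about 77% per comparison. Keeping 132 evaluable per arm instead would mean 495 randomised, which is 165 more than 330.
- **If one dose has been dropped:** replace the three-arm and 1:1:1 wording with the actual Stage 2 allocation. Show that 132 per remaining arm does not count subjects already in the dropped arm.

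In both cases, explain which of 11.51/27.3 and 15/34.83 governs and why, and reconcile 122 and 153 per treatment with 132 and 330. The SAP says it supersedes the protocol's statistical methods, but protocol 6.1 requires changes to principal features to go through a protocol amendment, so both documents need the edit.

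The cost is wording in the protocol and SAP, and a less favourable stated power if 330 in three arms is kept. Restating needs no additional patients.
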